### 3. Provide a justification for the sample size used in this protocol.

**Table 1. Detectable Differences in Powered Minus Unpowered Walker Outcomes.**

Outcome Measure	Standard Deviation of Paired Differences	Paired Data Correlation	Detectable Difference ( $\Delta$ )	Detectable Effect Size
Oxygen Consumption	4.61 mL/kg/min	0.256	-3.0 mL/kg/min	0.65
Walking Speed	4.16 m/min	0.963	3.5 m/min	0.85
Device Acceptance	2.26 units	-0.019	1.3 units	0.58

Power analysis: Assuming a significance level of  $\alpha=0.05$ , based on the standard deviations of paired differences listed in column 2 of Table 1 and the empirical measurement correlations in column 3 of Table 1, a one-sided paired t-test achieve 80% power to detect a mean of the paired differences listed in column 4 of Table 1. These represent medium-to-large effect sizes (column 5 of Table 1), but magnitudes that we would expect to achieve under the alternative hypothesis.

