**Subjects- see below**

**1. Provide target # of subjects (at all sites) needed to complete protocol.**

48 subjects total, 24 individuals with CP and 24 typically developed subjects.

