### 4. What is your plan for primary variable analysis?

Include a sketch of the analysis to assess primary study objectives.

Each patient will provide one trial of unpowered walker data and two trials of powered walker data. Thus, a total of two *difference* combinations (*i.e.*, *powered minus unpowered outcomes*) for each of 10 patients will yield 20 difference ( $\Delta$ ) values for *each* outcome measure:  $\Delta_{\text{oxygen}}$  consumption,  $\Delta_{\text{walking speed}}$ , and  $\Delta_{\text{device acceptance}}$ . To assess the unpowered to powered walker changes in outcomes based on each set of 20 pooled  $\Delta$  values, a one-sided paired t-test will be used to test the following null hypothesis:  $H_0: \Delta_{\text{oxygen consumption}} = 0$  versus the alternative hypothesis  $H_a: \Delta_{\text{oxygen consumption}} < 0$ ;  $H_0: \Delta_{\text{walking speed}} = 0$  versus the alternative hypothesis  $H_a: \Delta_{\text{walking speed}} > 0$ ; and  $H_0: \Delta_{\text{device acceptance}} = 0$  versus the alternative hypothesis  $H_a: \Delta_{\text{device acceptance}} > 0$ .

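### Table 1's 80% power for device acceptance rests on a within-patient correlation of -0.019, which the shared unpowered trial makes hard to defend; on the 10-patient basis any clearly positive value gives less than 80%.

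*Combined protocol and SAP*

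**What the plan says.** Statistical Considerations, item 3, bases its power statement on Table 1. For each outcome the table gives an SD of paired differences, a correlation, a detectable difference and an effect size. At alpha 0.05 the text claims that, based on those SDs and "the empirical measurement correlations in column 3 of Table 1, a one-sided paired t-test achieve 80% power" at the differences in column 4. It gives neither the source of those correlations nor a sample size.

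Item 4 supplies the design: "Each patient will provide one trial of unpowered walker data and two trials of powered walker data". Two differences per patient, "for each of 10 patients will yield 20 difference" values per outcome, go into a one-sided paired t-test. The enrolment target under Subjects is larger: "48 subjects total, 24 individuals with CP and 24 typically developed subjects".

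**The concern.** Each patient's two differences subtract the same unpowered measurement. An error in that one measurement moves both differences the same way, which pushes their correlation upwards. A correlation of -0.019 says instead that the second difference is as informative as a new patient. If that is too optimistic, 10 patients carry less information on device acceptance than Table 1 credits, and its 80% at 1.3 units is overstated.

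Table 1 is the only power statement in the plan. Item 2 defines success as improvement on oxygen consumption, walking speed and device acceptance together, so a weak acceptance row limits the chance of overall success.

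**Working it through.** **Inputs.** From Table 1: SD of differences 4.61, 4.16 and 2.26; column 3 values 0.256, 0.963 and -0.019; detectable differences 3.0, 3.5 and 1.3 (oxygen, speed, acceptance). From item 3: one-sided alpha 0.05, power 80%. From item 4: 10 patients, two differences each.

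**Step 1: reproduce Table 1.** The mean of a patient's two differences has variance SD² × (1 + rho)/2. Over 10 patients the variance of the overall mean is SD² × (1 + rho)/20, so the effective sample is n_eff = 20/(1 + rho). Power comes from the noncentral t with n_eff - 1 degrees of freedom and noncentrality (difference/SD) × √n_eff.

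| Outcome | n_eff | Difference at 80% power | Table 1 | Power at Table 1 value |
|---|---|---|---|---|
| Oxygen | 20/1.256 = 15.9 | 3.01 | 3.0 | 79.7% |
| Speed | 20/1.963 = 10.2 | 3.51 | 3.5 | 79.8% |
| Acceptance | 20/0.981 = 20.4 | 1.29 | 1.3 | 80.5% |

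Rounding n_eff to 16, 10 and 20 also returns the printed effect sizes: 0.65, 0.85 and 0.58. A single n for all rows does not work: n = 20 gives 0.58 throughout and n = 10 gives 0.85 throughout. Column 3 was therefore used as the correlation between a patient's two differences.

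The other natural meaning is the correlation between powered and unpowered readings. That correlation is already inside the SD of the differences and would not enter again. The three rows would then need three different sample sizes.

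**Step 2: what the shared trial implies for rho.** Let U be the unpowered trial and P1, P2 the powered trials. Assume P1 and P2 have equal variance and the same correlation r_PU with U, and let r_PP be the correlation between them. Then

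rho = [Var(U) + Cov(P1,P2) - 2 Cov(P,U)] / Var(difference).

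With SD(U) = 1 and SD(P) = s, where s may be any value, the numerator is 1 + r_PP s² - 2 r_PU s. If r_PP ≥ r_PU ≥ 0, this is at least (1 - r_PU) + r_PU (1 - s)², which is positive except in the degenerate case r_PU = 1, s = 1. A value at or below zero therefore needs r_PP < r_PU (taking r_PU as non-negative). For example, equal SDs with r_PP = 0.6 and r_PU = 0.8 give (1 + 0.6 - 1.6)/(2 - 1.6) = 0. With equal SDs and one common correlation r, rho = (1 - r)/(2 - 2r) = 0.5.

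**Step 3: device acceptance with 10 patients.** The documents give no other rho, so these values are assumptions shown as a range.

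| rho | n_eff | Power at 1.3 units | Difference at 80% power |
|---|---|---|---|
| 0.1 | 18.2 | 76% | 1.4 |
| 0.3 | 15.4 | 69% | 1.5 |
| 0.5 | 13.3 | 63% | 1.6 |
| 0.75 | 11.4 | 57% | 1.8 |

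Analysing patient means with 9 degrees of freedom gives slightly less (62% at rho 0.5).

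**Step 4: the other rows.** Oxygen at rho 0.5: power at 3.0 is 72.5% and the 80% difference is 3.3 mL/kg/min. Speed already uses 0.963.

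**Step 5: 24 patients.** By patient means, n_eff = 48/(1 + rho) with 23 degrees of freedom. Acceptance power at 1.3 units is 93% at rho 0.5 (n_eff = 32) and 86% at rho 1 (n_eff = 24).

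**The case against.** The strongest reply is that the correlations are described as empirical and that the printed 80% follows from them. Both are true: the arithmetic of Table 1 is sound, and the point concerns an input. A small pilot could also produce -0.019 by chance. If the true value were 0.5, a 10-patient pilot (an assumed size) would show -0.019 or lower about 5% of the time. But sampling noise of that order is a reason not to plan on the point estimate when the design points to a positive value.

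A reader might infer that the shared trial forces a correlation of at least 0.5, so that -0.019 is impossible and the oxygen row is wrong too. The documents do not support this. The 0.5 needs equal variances and one common correlation, and neither is stated. Equal SDs with r_PP = 0.7 and r_PU = 0.8 give (1 + 0.7 - 1.6)/0.4 = 0.25, almost exactly the oxygen value. The hypotheses describe an adaptive learning controller, so the two powered trials need not be replicates of each other.

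It can also be said that item 4 plans a t-test on the 20 pooled values with no allowance for correlation, so the powers in step 3 belong to a different test. In simulation at rho 0.5 the pooled test rejects 83.5% of the time for oxygen and 76% for acceptance. Acceptance still falls short of 80%, and the pooled test gets there with a one-sided type I error of about 9% instead of 5%.

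Finally, a reader might infer that the trial is underpowered. With the 24 CP subjects of the enrolment target, power exceeds 80% for oxygen and acceptance at every correlation up to 1. This stands: the shortfall belongs to the 10-patient analysis alone.

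**Conclusion.** The point holds for one row. On the 10-patient basis that reproduces Table 1, 80% power at 1.3 units of device acceptance needs a correlation of about zero or below. The documents give no reason to expect the two powered trials to agree less with each other than with the unpowered one. Over rho 0.1 to 0.75 power is about 76% to 57%, and the 80% detectable difference is 1.4 to 1.8 units.

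This rests on column 3 having the role that reproduces the table, on powered trials of equal variance and equal non-negative correlation with the unpowered trial, and on assumed values of rho. The oxygen row is not shown to be wrong. The finding affects a stated figure and does not show that the enrolment target is too small.

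**What to change.** - Reconcile the 10 patients in item 4 with the 24 CP subjects in the enrolment target, and state the number on which Table 1 rests.
- State what column 3 measures and the size and design of the dataset behind it.
- In the acceptance row, do not use a correlation at or below zero. Give power at 1.3 units, or the detectable difference, over a positive range such as 0.3 to 0.75. For 10 patients that is 69% to 57%, or 1.5 to 1.8 units.
- Add one sensitivity line for oxygen at rho 0.5. Leave walking speed as it is.

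Switching to the SD of each patient's mean difference would not avoid the question. It combines columns 2 and 3 algebraically and changes only the degrees of freedom.

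The cost is recalculating part of one table. On the 10-patient basis one stated figure becomes less favourable. No additional enrolment follows.

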**2. Describe expected rate of screen failure/ dropouts/withdrawals from all sites. 2**

**3. How many subjects will be enrolled at all sites? 50**

**4. How many subjects will sign a consent form under this UVa protocol? 50**

**5. Provide an estimated time line for the study.**

48 subjects were recruited in year 2.

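### Table 1's 80% power fits 10 patients, not the 24 CP / 48 subjects targeted, and the planned pooled t-test ignores the within-patient correlation that Table 1 appears to allow for (walking-speed type I error about 13%, not 5%)

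*Combined protocol and SAP*

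**What the plan says.** All references are to the combined protocol and SAP.

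- **Subjects, item 1** sets the target: "48 subjects total, 24 individuals with CP and 24 typically developed subjects". Item 5 of the same section reports that "48 subjects were recruited in year 2".
- **Statistical Considerations, item 3**, which is meant to justify the sample size, gives Table 1 and states that "a one-sided paired t-test achieve 80% power to detect a mean of the paired differences listed in column 4 of Table 1". It says the calculation also uses "the empirical measurement correlations in column 3 of Table 1". It prints no number of subjects, no formula and no definition of that correlation.
- **Statistical Considerations, item 4** gives the design of the primary analysis: "Each patient will provide one trial of unpowered walker data and two trials of powered walker data". Two differences "for each of 10 patients will yield 20 difference" values per outcome. The test is applied "To assess the unpowered to powered walker changes in outcomes based on each set of 20 pooled" differences. It is one-sided, and no allowance is stated for two values coming from the same patient.

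**The concern.** Two things do not match.

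1. **The n.** The section that should support 24 and 48 supports neither, and the analysis section uses 10. Nothing connects 10 to 24 or 48, or says which 10 patients are analysed. The primary analysis could be run on 10, 24 or 48 subjects, and each choice can be defended from some part of the text. If this is not settled beforehand, it may be settled once data are available.

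2. **The test.** Table 1 appears to reduce the 20 differences for within-patient correlation, but the planned t-test counts them as 20 independent values. The standard error is then too small wherever that correlation is positive, and the test rejects too often. Walking speed, with 0.963 in column 3, is the most exposed.

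**Working it through.** **Inputs (Table 1; item 4).** One-sided α = 0.05. SDs of differences are 4.61, 4.16 and 2.26. Column 3 values are 0.256, 0.963 and −0.019. Detectable differences are 3.0 (a reduction), 3.5 and 1.3. There are 10 patients with two differences each.

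**Step 1: reproduce the 80%.** Standardised effects d = difference/SD are 3.0/4.61 = 0.651, 3.5/4.16 = 0.841 and 1.3/2.26 = 0.575. Power is P(T > t₀.₉₅,ₙ₋₁), where T is noncentral t with n − 1 df and noncentrality d√n.

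| n used | Oxygen | Speed | Acceptance |
|---|---|---|---|
| 10 | 60.1% | 79.1% | 51.4% |
| 20, no discount | 87.7% | 97.6% | 79.8% |
| 24 | 92.6% | 99.1% | 86.2% |
| 48 | 99.7% | >99.9% | 98.9% |
| 20/(1+r) = 15.9 / 10.2 / 20.4 | 79.7% | 79.8% | 80.5% |

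The n needed for exactly 80% is 16.0, 10.2 and 20.1. Only 10 patients × 2 differences with design effect 1 + r matches all three rows, and the three correlations are very different.

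**Step 2: the same calculation at the 24 CP subjects.** Effective n = 48/(1+r) = 38.2, 24.5 and 48.9. Power at Table 1's differences is 98.9%, 99.2% and 99.0%. If the second difference added nothing (r = 1), n is 24 and power is still 92.6%, 99.1% and 86.2%. So 24 exceeds what Table 1 requires, however column 3 is read.

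**Step 3: type I error of the test as planned.** The pooled t-test uses s²/20 as the variance of the mean, but the true variance is about σ²(1+r)/20. For large samples the actual one-sided level is therefore 1 − Φ(1.645/√(1+r)):

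- oxygen: 1.645/√1.256 = 1.468, level 7.1%
- speed: 1.645/√1.963 = 1.174, level 12.0%
- acceptance: 1.645/√0.981 = 1.661, level 4.8%

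Simulation (200,000 trials each) gives 7.2%, about 13% and 4.8% with 10 patients. With 24 patients and 48 values it gives about 7%, 12% and 5%, so a larger sample does not cure the problem. A t-test on each patient's mean difference holds 5% throughout.

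**Step 4: power of the patient-mean test.** The SD of a patient's mean difference is SD × √((1+r)/2) = 3.65, 4.12 and 1.58.

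| Patients (df) | Oxygen | Speed | Acceptance |
|---|---|---|---|
| 10 (9): power at Table 1's differences | 77.3% | 79.7% | 77.3% |
| 11 (10): same | 81.3% | 83.5% | 81.3% |
| 24 (23): same | 98.8% | 99.2% | 98.8% |
| 24 (23): difference detectable with 80% power | 1.91 mL/kg/min | 2.16 m/min | 0.83 units |

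The last row is 36% to 38% below Table 1's differences.

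**The case against.** **Column 3 may mean something else.** Its label and the accompanying text could describe a correlation between powered and unpowered measurements. The three-row fit is strong evidence for the reading used here, but it is not a definition. Both differences also subtract the same single unpowered trial. If all trials have equal variance σ² and equal correlation c (an assumption), the covariance of the two differences is σ²(1 − c) and their variance is 2σ²(1 − c), so their correlation is 0.5. Table 1's 0.256 and −0.019 sit oddly with that. This part stands, and it makes the figures for oxygen and acceptance less secure. It does not rescue the plan: at r = 0.5 the pooled test rejects about 9% of the time, and the differences detectable with 24 patients become about 2.09 mL/kg/min, 1.88 m/min and 1.02 units.

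**The study is larger than it needs to be.** This is correct; it is not underpowered for Table 1's differences. The target is still unexplained and the analysed number still contradictory.

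**Success requires all three outcomes (item 2), which limits a false overall claim.** This holds if none of the three effects is real. If oxygen and acceptance truly improve and are very likely to be detected, nearly all of the walking-speed error carries through. Each outcome also has its own test in item 4.

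**The Study Design section plans a repeated measures ANOVA.** That is a within-subject method, but it is offered for global effects and does not replace the t-test in item 4.

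**Conclusion.** The concern holds. That the analysis plan uses 10 patients while the target is 24 CP and 48 in total, with no n in the sample-size section, is plain from the text and needs no assumption. That Table 1 was computed for 10 patients with a correlation discount is an inference, though a close one: it returns 79.7% to 80.5% in all three rows, and none of n = 10, 20, 24 or 48 without a discount does. Table 1's arithmetic is sound on that basis; the fault is that it supports neither the enrolment target nor the planned test.

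On the same reading, the walking-speed test has a type I error of about 13% with 10 patients, roughly 2.5 times nominal. Oxygen is modestly inflated at about 7% and acceptance is not inflated. If column 3 is the powered–unpowered correlation instead, the correlation between differences is not given; over an assumed range of 0.5 to 0.963 the error with 10 patients is about 9% to 13%. This should be fixed, because it affects the validity of a primary test and the rationale for the sample size.

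**What to change.** 1. Name one primary analysis set and one n, and use them in both items 3 and 4 of Statistical Considerations.
2. Define column 3 and print the power formula.
3. Replace the t-test on pooled differences with a one-sided t-test on each patient's mean of the two differences. State how this relates to the repeated measures ANOVA in the Study Design section.
4. Restate Table 1 for the chosen set:
   - **24 CP subjects (23 df):** detectable differences of −1.91 mL/kg/min, 2.16 m/min and 0.83 units, or keep Table 1's differences and state about 99% power for each outcome. These figures assume column 3 is the correlation between a patient's two differences; recompute them if it is defined otherwise.
   - **10 patients (9 df):** explain why 24 and 48 are enrolled, and how the 10 are fixed before outcome data are seen. Power is then about 77%, 80% and 77%; 11 patients give at least 80% in every row.

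The cost is a revised table, a sentence fixing the analysis set and n, and a one-line change of test. No additional patients are needed, since 24 CP subjects are already in the target.

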### 4. What is your plan for primary variable analysis?

Include a sketch of the analysis to assess primary study objectives.

Each patient will provide one trial of unpowered walker data and two trials of powered walker data. Thus, a total of two *difference* combinations (*i.e.*, *powered minus unpowered outcomes*) for each of 10 patients will yield 20 difference ( $\Delta$ ) values for *each* outcome measure:  $\Delta_{\text{oxygen}}$  consumption,  $\Delta_{\text{walking speed}}$ , and  $\Delta_{\text{device acceptance}}$ . To assess the unpowered to powered walker changes in outcomes based on each set of 20 pooled  $\Delta$  values, a one-sided paired t-test will be used to test the following null hypothesis:  $H_0: \Delta_{\text{oxygen consumption}} = 0$  versus the alternative hypothesis  $H_a: \Delta_{\text{oxygen consumption}} < 0$ ;  $H_0: \Delta_{\text{walking speed}} = 0$  versus the alternative hypothesis  $H_a: \Delta_{\text{walking speed}} > 0$ ; and  $H_0: \Delta_{\text{device acceptance}} = 0$  versus the alternative hypothesis  $H_a: \Delta_{\text{device acceptance}} > 0$ .

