**3. List any restrictions on use of other drugs or treatments. None**

## Statistical Considerations

### 1. Is stratification/randomization involved? No

### 2. What are the statistical considerations for the protocol?

BAI and UVA will work together to prepare the trial results for statistical analysis. The analysis shall include testing for within-subject differences of oxygen consumption, walking speed, and device acceptance scores based on participant's use of the baseline (unpowered) and powered walkers. Past experience by the BAI/UVA team gives us the qualifications to complete statistical analyses in-house. Success will be defined by the controlled/powered walker significantly reducing oxygen consumption, increasing walking speed, and having superior device acceptance compared to the unpowered walker.

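### The primary t-test counts two differences per patient as independent, so its one-sided error exceeds 5% whenever those differences are positively correlated

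*Combined protocol and SAP*

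**What the plan says.** Statistical Considerations, item 4 (primary variable analysis) sets the data structure: "Each patient will provide one trial of unpowered walker data and two trials of powered walker data". Taking powered minus unpowered twice "for each of 10 patients will yield 20 difference" values per outcome. The tests are run "based on each set of 20 pooled" values, and for these "values, a one-sided paired t-test will be used to test the following null hypothesis". No averaging within patient, clustering correction or patient effect is given.

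Item 3 (sample size) says the power analysis used "the empirical measurement correlations in column 3 of Table 1", and that "a one-sided paired t-test achieve 80% power to detect a mean of the paired differences listed in column 4 of Table 1". It does not say which pair of measurements column 3 describes.

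Item 2 sets the success rule: "Success will be defined by the controlled/powered walker significantly reducing oxygen consumption, increasing walking speed, and having superior device acceptance". The enrolment target is "48 subjects total, 24 individuals with CP and 24 typically developed subjects". The Study Design section mentions repeated measures ANOVA for global effects, but item 4 does not use it for the primary tests.

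**The concern.** A patient's two differences share the patient and also the single unpowered measurement that is subtracted. An unusually poor unpowered trial makes both differences look good. Twenty such values generally do not carry the information of 20 independent ones, yet a t-test on the pooled set uses 19 degrees of freedom and a standard error that assumes they do. For any outcome with r > 0, the p-value is too small, and so is the width of any confidence interval built the same way.

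These three tests decide the study, and no secondary analysis is planned. Requiring all three to succeed makes a joint false success rare when nothing improves. It does not repair the individual tests. If two outcomes truly improve and the third does not, the success claim turns on that third test, whose error is inflated.

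**Working it through.** **Inputs.** From item 4: 10 patients, two differences each, one-sided tests. From item 3: alpha 0.05 and 80% power. From Table 1 (oxygen, speed, acceptance): SD of differences 4.61, 4.16, 2.26; column 3 correlations 0.256, 0.963, −0.019; detectable differences 3.0 (a reduction), 3.5, 1.3. The within-patient correlation r of the two differences is not stated.

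**Step 1: reproduce Table 1.** Solve the noncentral t for 80% power, one-sided 0.05, and multiply by the SD. Candidate sample sizes are 20 independent values, 10 patients, and an effective n of 20/(1 + column 3):

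- 20/1.256 = 15.9
- 20/1.963 = 10.2
- 20/0.981 = 20.4

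| Outcome | Printed | n = 20/(1 + column 3) | n = 20 | n = 10 |
|---|---|---|---|---|
| Oxygen | 3.0 | 3.01 | 2.66 | 3.93 |
| Speed | 3.5 | 3.51 | 2.40 | 3.55 |
| Acceptance | 1.3 | 1.29 | 1.30 | 1.93 |

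Of these, only the effective-n version matches all three rows. So the power calculation appears to treat column 3 as r and to discount for it, while the planned test does not. This is an inference from the arithmetic.

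**Step 2: what r could be.** Let ρPP be the correlation between the two powered trials and ρPU that between a powered and the unpowered trial. With equal variances,

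r = (1 + ρPP − 2ρPU) / (2(1 − ρPU)).

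If ρPP = ρPU, then r = 0.5 whatever their common value. If ρPP is larger, r exceeds 0.5; if smaller, r is below 0.5.

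**Step 3: standard error.** With SD σ, the mean of the 20 values has variance σ²(1 + r)/20, against σ²/20 if independent. The true standard error is √(1 + r) times the independent one: 1.12, 1.40 and 0.99 at the column 3 values, and 1.22 to 1.41 for r from 0.5 to 1.

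**Step 4: error of the pooled test.** The sum of squares about the pooled mean is σ²[(1 + r)χ²(9) + (1 − r)χ²(10)] for 10 patients. Simulating the t statistic against its 19-df one-sided 5% critical value gives:

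| r | 10 patients | 24 patients | 48 patients |
|---|---|---|---|
| −0.019 (acceptance, column 3) | 4.8% | 4.8% | 4.8% |
| 0.256 (oxygen, column 3) | 7.1% | 7.1% | 7.1% |
| 0.5 (assumed) | 9.2% | 9.0% | 9.0% |
| 0.75 (assumed) | 11.2% | 10.9% | 10.8% |
| 0.963 (speed, column 3) | 12.9% | 12.4% | 12.2% |
| 1 (assumed) | 13.2% | 12.6% | 12.4% |

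The 24- and 48-patient columns use the matching degrees of freedom. Values vary by about 0.1 point between simulation runs.

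**Step 5: one averaged difference per patient.** The simulated error of this test is 4.9% to 5.1% in every case tried. The SD of a patient's averaged difference is σ√((1 + r)/2): 3.65, 4.12 and 1.58 at the column 3 values. With n = 10 and 9 df, power for the printed differences is 77%, 80% and 77%.

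**The case against.** The mechanism is hard to dispute; the size is open to challenge.

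- **Column 3 is undefined.** Its ordinary meaning would be the powered–unpowered correlation. The match in Step 1 is to rounded values, and only oxygen and speed discriminate. It also sits awkwardly with the shared unpowered trial: under equal variances, r below 0.5 needs the two powered trials to agree less with each other than with the unpowered one. This stands. If column 3 is not r, values near or above 0.5 would mean more inflation for oxygen and acceptance, not less.
- **r could be negative.** If 0.963 is the powered–unpowered correlation for speed, any powered–powered correlation below 2 × 0.963 − 1 = 0.926 makes r negative and the pooled test conservative: about 2% error at 0.9. This stands, and it is why the finding is conditional on r > 0. The test's level still depends on a quantity the plan does not give.
- **All three outcomes must succeed.** Assuming independent outcomes, 10 patients, column 3 as r, and the other two outcomes truly at their Table 1 differences, joint false success is about 5% (oxygen null), 9% (speed null) and 4% (acceptance null). So at 10 patients the rule absorbs part of the inflation. With 24 patients the joint rates come close to the individual ones.
- **Item 4 is only a sketch, and the plan elsewhere names repeated measures ANOVA.** The unit of analysis is nonetheless explicit, and the ANOVA is not assigned to these tests. Nor does item 4 plan a confidence interval, so that consequence applies only if one is reported.

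**Conclusion.** The concern holds and must be fixed before analysis. As written, the primary test does not guarantee its 5% one-sided level. Its error exceeds 5% for any outcome whose two within-patient differences are positively correlated, at any number of patients. If column 3 of Table 1 is that correlation, error is about 7% for oxygen and 13% for speed, with acceptance unaffected at 4.8%. If r lies between 0.5 and 1, error is about 9% to 13%. These figures assume normal differences with equal variances. Confidence is high in the mechanism; the exact size depends on an r the documents do not state.

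**What to change.** In item 4, replace the pooled-values wording with: average each patient's two powered trials, subtract the unpowered trial, and apply the one-sided paired t-test to one difference per patient, with df equal to patients minus 1. In item 3, define the correlation in column 3 and restate power for this test at the number of patients to be analysed. That number needs settling, since item 4 uses 10 and the enrolment target is 24 + 24.

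State how this test relates to the repeated measures ANOVA in Study Design. Do not use a standard three-trial compound-symmetry ANOVA in its place. At 10 patients its powered-minus-unpowered contrast has error of about 3% at r = 0.256, 5% at 0.5, 8.2% at 0.75 and 11.8% at 0.963, so it too depends on r.

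No new data are needed. P-values become less favourable where r > 0. At 10 patients, power for the printed differences is 77% (oxygen), 80% (speed) and 77% (acceptance) at the column 3 values. For r from 0.5 to 1 it is 60–71%, 79–88% and 51–62%. With the 24 subjects with CP it is at least 86% for every outcome in all these cases.

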### **Hypothesis to be Tested**

Hypothesis: A powered posterior walker will have a significant effect on A) the mobility and B) the efficiency of the gait patterns for typically developed individuals and those of children with cerebral palsy

1. Hypothesis: An adaptive learning control algorithm can be implemented for a powered walker to develop optimal movement and efficiency in the gait patterns of typically developed individuals and those of children with cerebral palsy

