### **Study Design: Biomedical**

1. **Will controls be used?** Yes

► **IF YES, explain the kind of controls to be used.**

Matching gait analysis will be conducted on typically developed individuals with and without the walker

2. **What is the study design?**

This study design is a repeated measures crossover study. Repeated measures ANOVA will be performed to determine any global effects of the powered walker on the efficiency Kinematics, and force loads applied during walking.

3. **Does the study involve a placebo?** No

4.

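### The primary t-test is written for 10 patients and 20 pooled differences, while the trial targets 24 CP plus 24 typically developed subjects; the counts are not reconciled, no group is named for the success decision, and the pooled test ignores the pairing within patient

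*Combined protocol and SAP*

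**What the plan says.** Statistical Considerations item 4 is the only description of the primary test. It sets the data per person: "Each patient will provide one trial of unpowered walker data and two trials of powered walker data". Two powered-minus-unpowered differences "for each of 10 patients will yield 20 difference" values for each of oxygen consumption, walking speed and device acceptance. Each set of 20 is pooled and tested with a one-sided t-test. No term for patient is mentioned.

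The Subjects section gives other counts. Item 1 has "48 subjects total, 24 individuals with CP and 24 typically developed subjects". Item 3 has "How many subjects will be enrolled at all sites? 50". Item 5 states that "48 subjects were recruited in year 2".

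On the group, the Hypothesis section covers "the efficiency of the gait patterns for typically developed individuals and those of children with cerebral palsy". Study Design item 1 gives the typically developed subjects a control role: "Matching gait analysis will be conducted on typically developed individuals with and without the walker". Item 2 adds another analysis: "Repeated measures ANOVA will be performed to determine any global effects of the powered walker". The success rule in Statistical Considerations item 2 asks for improvement in oxygen consumption, walking speed and device acceptance. It names no group and does not mention the ANOVA.

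Statistical Considerations item 3 (Table 1) claims 80% power at one-sided 0.05 for each outcome, using the SDs of paired differences and the column 3 correlations. It states no n.

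**The concern.** An analyst holding data on 48 subjects cannot carry out item 4 as written. The test describes 10 people, and the plan does not say whether they are a subset, an earlier phase or a figure left over from a smaller study. The analyst would have to choose the number of subjects, and whether success is judged in the CP group, the typically developed group or both together. If that choice is made after the outcomes are known, the stated error rate no longer describes the decision.

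The second issue is the unit of analysis. Both differences from a patient subtract the same unpowered trial, so they may well be correlated. A t-test on 20 pooled values counts them as 20 independent observations. With positive correlation the standard error is too small and the test rejects too often.

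**Working it through.** **Inputs.** From Table 1, in the order oxygen / speed / acceptance: SD of paired differences 4.61 / 4.16 / 2.26; column 3 correlation r 0.256 / 0.963 / -0.019; detectable difference (absolute value) 3.0 / 3.5 / 1.3. One-sided alpha is 0.05. Item 4 gives 10 patients with 2 differences each. The correlation rho between a patient's two differences is not identified as such in the documents, so a range is shown.

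**Step 1: reproduce Table 1's 80%.** Standardised effects are d = 3.0/4.61 = 0.651, 3.5/4.16 = 0.841 and 1.3/2.26 = 0.575. Power comes from the noncentral t with n - 1 degrees of freedom and noncentrality d × sqrt(n).

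| n used | Oxygen | Speed | Acceptance |
|---|---|---|---|
| 10 | 60.1% | 79.1% | 51.4% |
| 20 | 87.7% | 97.6% | 79.8% |
| 20/(1+r) | 79.7% | 79.8% | 80.5% |

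Neither plain n gives 80% for all three outcomes. The last row does, with effective n of 20/1.256 = 15.9, 20/1.963 = 10.2 and 20/0.981 = 20.4. Its detectable differences are 3.01, 3.51 and 1.29, against 3.0, 3.5 and 1.3 in the table. The formula is inferred; item 3 says only that the correlations were used. On this reading column 3 is the correlation between a patient's two differences, and Table 1 describes the 10-patient design of item 4, with a discount for correlation that the t-test in item 4 does not make.

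**Step 2: error of the pooled test.** With N patients the mean of 2N pooled differences has variance SD² × (1+rho)/(2N), while the t-test assumes roughly SD²/(2N). The test statistic is therefore too variable by about sqrt(1+rho). The large-sample one-sided error is 1 - Φ(1.645/sqrt(1+rho)), which does not depend on N. Simulation at the two sample sizes gives:

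| rho | 10 patients, 20 values | 24 patients, 48 values | Large-sample formula |
|---|---|---|---|
| 0 | 5.0% | 5.0% | 5.0% |
| 0.25 | 7.1% | 7.0% | 7.1% |
| 0.5 | 9.2% | 9.0% | 9.0% |
| 0.75 | 11.2% | 10.9% | 10.7% |
| 1 (limit) | 13.2% | 12.7% | 12.2% |

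Taking column 3 as rho, with 10 patients, the error is about 7% (oxygen), 13% (speed) and 5% (acceptance, no inflation).

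**Step 3: one value per subject.** The mean of a subject's two differences has SD equal to the Table 1 SD × sqrt((1+rho)/2). The simulated error of a t-test on these means is 5% to within simulation error. At n = 24:

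- Power at rho = 1, the least favourable case: 92.6 / 99.1 / 86.2%. With column 3 as rho: 98.8 / 99.2 / 98.8%.
- The standardised difference detectable with 80% power is 0.523. With column 3 as rho: 0.523 × 4.61 × sqrt(1.256/2) = 1.9 mL/kg/min; 0.523 × 4.16 × sqrt(1.963/2) = 2.2 m/min; 0.523 × 2.26 × sqrt(0.981/2) = 0.83 units.
- For rho from 0 to 1: 1.7 to 2.4 mL/kg/min, 1.5 to 2.2 m/min and 0.84 to 1.2 units. (The 0.83 falls just below this range because acceptance has a slightly negative r.)

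**The case against.** Four points can fairly be made for the plan.

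- **The intended group can be guessed.** Item 4 speaks of patients and Study Design labels the typically developed subjects as controls, so CP is the natural reading. This stands as a hint. It is not stated, the hypothesis covers both groups, and 10 still does not equal 24. That the choice might follow the data is a possibility left open; the documents do not show that it happened.
- **The power calculation is internally coherent.** Table 1 is reproduced by one formula on 10 patients. This stands. A reader might infer from the plain t-test that each row of Table 1 uses a different n and that the table is inconsistent; step 1 does not support that. Nor does the charge of treating values as independent extend to Table 1, which appears to discount for correlation.
- **Success appears to need all three outcomes.** This also stands. The 7% to 13% figures are errors per test and should not be read as the chance of a false overall success when the walker has no effect on any outcome. An inflated test drives the decision mainly when the other two effects are real.
- **The sample may be ample.** It is. A reader might infer that the trial is underpowered. With 24 subjects that is wrong for the Table 1 effects. Even with 10 patients analysed by their means, power on the column 3 reading is 77 / 80 / 77%, a slight shortfall at most.

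It is also tempting to derive a minimum rho from column 3 by reading it as the correlation between powered and unpowered trials. The column label does not settle that meaning, and the reading that reproduces the table is a different one, so no such minimum is claimed here.

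**Conclusion.** The point holds and should be corrected before the results are relied on. Two parts need no assumption: the primary test is written for a sample that is not the trial's (10 against 24 + 24), and no group is named for the success decision. The third part is conditional. The pooled t-test exceeds its one-sided 5% whenever a patient's two differences are positively correlated, reaching about 7% to 13% per test for correlations of 0.25 to 1, and a larger sample does not remove this. If column 3 is that correlation, speed is the worst affected, oxygen moderately, and acceptance not at all. That the sample-size justification also belongs to 10 patients rests on an inferred formula, though one that recovers all three rows. Low power is not part of the conclusion.

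**What to change.** **Statistical Considerations item 4.** Replace the sentence on 10 patients and 20 values with wording such as: *For each outcome, each subject contributes one value, the mean of the two powered trials minus the unpowered trial. A one-sided t-test on these values in the 24 subjects with CP decides success. The two groups are not pooled for this decision.* The sponsor may name a different group, but should do so before analysis.

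**Study Design item 2.** State whether the repeated measures ANOVA has any part in the success decision.

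**Statistical Considerations item 3.** State the n, say what column 3 measures, and restate the detectable differences for that n. At 24 subjects and 80% power they are the figures in step 3: about 1.9 mL/kg/min, 2.2 m/min and 0.83 units if column 3 is the correlation between a patient's two differences, otherwise the ranges given there. Both assume that the Table 1 SDs apply to the group tested.

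**Cost.** Wording and a recalculated table, with no new CP data, provided all 24 CP subjects complete the one unpowered and two powered trials. Reporting the same contrast in the typically developed group depends on whether they complete those trials; Study Design plans gait analysis with and without the walker and does not say so. Recruitment is already reported as done, so if analysis has begun, the change should be documented as made after that point.
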